3 DATA ANALYSIS CONSIDERATIONS

3.1 General presentation of summaries and analyses

Statistical analysis and generation of tables, figures, participant data listings, and statistical output will be performed using SAS® Version 9.3 or higher. All tables and listings will use Courier New font size 9.

Descriptive statistics will be displayed to provide an overview of the study results. For continuous variables, descriptive statistics will include number of participants with available measurements (n), mean, SD, median, minimum, and maximum.

For categorical variables, the number and percentage of participants in each category will be presented. Unless otherwise noted, the denominator for percentages will be based on the number of participants included in the respective analysis set. Participants with missing data can generally be accounted for using the following approaches:

- For summaries of demographics and Baseline characteristics: summarize percentages based on all participants in the analysis set and include a “Missing” category (corresponding to participants with missing data for the variable being summarized) as the last row in the list of categories being summarized.
- For summaries of efficacy and safety variables, unless otherwise specified: summarize percentages based only on those participants with observed data for the variable being summarized. As the denominator may be different from the number of participants in the analysis set being considered, the denominator should be displayed in the table. The general format for displaying this will be “n/Nsub (%)”

Unless otherwise noted, all percentages will be displayed to one decimal place. No percentage will be displayed for zero counts, and no decimal will be presented when the percentage is 100%.

For the purpose of the tabulations the lower and upper confidence limits for the percentages will be truncated at 0 and 100% respectively.

Statistical tests of efficacy variables will be presented as p-values rounded to three decimal places. P-values less than 0.001 will be presented as “<0.001” and p-values greater than 0.999 will be presented as “>0.999”. Statistical comparisons will be two-sided and will be performed at the 0.05 level of significance unless specified otherwise. The significance levels used as part of the multiple testing procedure are detailed in [Section 4.6](#).

For PK concentrations, summary statistics will include geometric mean, geometric coefficient of variation (geoCV), 95% confidence intervals (CIs) for geometric mean, arithmetic mean, SD, median, minimum, and maximum. All summaries of PK variables will be based on the observed values. No imputation will be used.

Decimal places for descriptive statistics will always apply the following rules:

- “n” will be an integer;
- Mean, SD, and median will use one additional decimal place compared to the original data;
- CV [%] will be presented with one decimal place;
- Minimum and maximum will have the same number of decimal places as the original value.

If no participants have data at a given time point, for example, then only n=0 will be presented. However, if n<3, present the n, minimum and maximum only. If n=3, n, mean, median, minimum and maximum will be presented only. The other descriptive statistics will be left blank.

Derived variables in general will display the mean, SD and median to 1 more decimal place than the variables used in the derivation. If the number of decimal places reported in the raw data is varied, then use either the maximum raw number of reported decimal places or 3, whichever is the lowest, as a guide for the descriptive statistics.

3.2 General study level definitions

3.2.1 Analysis time points

All data will be analyzed based on the visits identified per the Schedule of Activities in protocol. Mapping to analysis visit windows is not applied, except for premature end of treatment (PEOT) visits (specified in [Section 3.2.3](#)).

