5. Study participants who complete the Treatment Period and require initiation of rescue therapy after they start the 8-week Observation Period, may either opt to receive IVIg or PEX or complete the End of Study (EOS) visit and immediately roll over into an OLE study where the participant will receive rozanolixizumab. Study participants who opt to receive IVIg or PEX will complete any remaining visits in the Observation Period and will not be invited to join an OLE study.
6. Study participants who did not complete the 6-week Treatment Period because they needed rescue therapy and require initiation of a second course of rescue therapy while in the 8-week Observation Period can roll over to an OLE study if a minimum of 2 weeks have lapsed since completion of the last IVIg or PEX session. The EOS visit must be completed before enrolling into an OLE study. Alternatively, they can be treated with IVIg or PEX. Study participants who opt to receive IVIg or PEX will complete any remaining visits in the Observation Period and will not be invited to join an OLE study.
7. Study participants who discontinue study medication for any reason other than requiring rescue therapy will not be eligible for enrollment into an OLE study.

Number of Participants

A formal interim analysis will be conducted when approximately [REDACTED] eligible study participants have been treated and are evaluable for the primary endpoint, ie, approximately [REDACTED] study participants per dose group. If the study is not stopped for futility after the interim analysis, then depending upon the selection of one, or two, of the doses after the interim analysis and the calculation of conditional power, a further [REDACTED] eligible study participants will be randomized into the study. Thus, the total sample size of the study could range between [REDACTED] and [REDACTED] study participants if the study is not futile (for sample size determination, see Section 9.9).

Treatment Groups and Duration

The maximum duration of the study per study participant will be up to 18 weeks, consisting of a Screening Period (1 to 28 days to account for central laboratory turn-around time), a Treatment Period (6 weeks), and an Observation Period (8 weeks).

Fixed unit doses across body weight tiers and study arms will be employed.

The placebo arm will be 0.9% sodium chloride aqueous solution (physiological saline, preservative free) for subcutaneous (sc) administration.

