active for MG0007, no further participants will enroll in MG0004 and the study will be closed at the site once all eligible study participants have discontinued MG0004 and had the opportunity to rollover into MG0007.

The maximum duration of the study per study participant will be up to 18 weeks, consisting of a Screening Period (1 to 28 days to account for central laboratory turn-around time), a Treatment Period (6 weeks), and a blinded Observation Period (8 weeks).

1. All study participants who complete the 6-week Treatment Period will roll over into an 8-week Observation Period.
2. All eligible study participants who complete the Observation Period will be invited to be re-randomized into an OLE study to either active dose arm 1 or 2.
3. Study participants who experience disease worsening during the 6-week Treatment Period (eg, an increase of 2 points on the MG-ADL or 3 points on the QMG scale between two consecutive visits) may be considered for rescue therapy (IVIg or PEX) at the discretion of the Investigator.
4. Study participants who need rescue therapy during the 6-week Treatment Period will receive IVIg or PEX and complete any subsequent visit(s). No further infusions of rozanolixizumab will be administered after initiation of rescue therapy. Once the participant completes Visit 10, he or she will move into the 8-week Observation Period.
5. Study participants who complete the Treatment Period and require initiation of rescue therapy after they start the 8-week Observation Period, may either opt to receive IVIg or PEX or complete the EOS visit and immediately roll over into an OLE study where the participant will receive rozanolixizumab. Study participants who opt to receive IVIg or PEX will complete any remaining visits in the Observation Period and will not be invited to join an OLE study.
6. Study participants who did not complete the 6-week Treatment Period because they needed rescue therapy and require initiation of a second course of rescue therapy while in the 8-week Observation Period can roll over to an OLE study if a minimum of 2 weeks have lapsed since completion of the last IVIg or PEX session. The EOS visit must be completed before enrolling into an OLE study. Alternatively, they can be treated with IVIg or PEX. Study participants who opt to receive IVIg or PEX will complete any remaining visits in the Observation Period and will not be invited to join an OLE study .

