4.2 Scientific Rationale for Study Design

MG0003 is designed to evaluate the efficacy, safety, and tolerability of rozanolixizumab given in dose exposures at [REDACTED] or [REDACTED] in study participants with MG. The previously conducted FIH study, UP0018, provided the safety, tolerability, and PK information for multiple dose exposures of [REDACTED] administered as iv or sc infusion over [REDACTED] in healthy volunteers.

The duration of the Treatment and Observation Periods were defined based on data from UP0018 and MG0002. In UP0018, results showed that upon administration of rozanolixizumab, the mean percentage change in total IgG over time demonstrated dose-dependent reductions across both the iv and sc routes of administration. Similar maximal reductions were observed for both the rozanolixizumab iv and sc doses (approximately 48% and 43%, respectively). The lowest level of IgG at maximum dose (both iv and sc) was reached by Day 10 on average. The total IgG levels generally returned to Baseline values by Day 57 on average.

Results from MG0002 showed that sc administration of rozanolixizumab resulted in a rapid reduction of serum IgG concentrations (Section 4.2.4.4), which also showed the greatest reductions from Baseline in QMG, MG-C, and MG-ADL after 6 infusions (Day 50). Therefore, a treatment duration of 6 weeks has been selected for MG0003 to ensure the maximum treatment effect of rozanolixizumab is captured. An 8-week Observation Period was defined in order to follow the recovery of IgG and AChR and MuSK antibodies, as well as monitoring the sustainability of the clinical effects after discontinuation.

The population in this study has been defined to exclude participants with severe weakness affecting oropharyngeal or respiratory muscles, or who have myasthenic crisis at Screening, as these participants would require urgent care incompatible with participation in the clinical study. This keeps consistent with the intended indication.

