4.4 End of Study definition

A study participant is considered to have completed the study if he/she has completed all phases of the study including the Observation Period. Study participants will have an EOS Visit performed 8 weeks after the last dose of study medication, or upon discontinuation of the study. The EOS is defined as the date of the last visit of the last study participant in the study.

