4.2 Handling of dropouts or missing data

4.2.1 Efficacy data

The rules for handling missing data of individual items in the calculation of the QMG, MG-C, MG-ADL, MG Symptom PRO, MGII, and MG-QOL15r scores at a certain visit are described in [Section 13.1](#), [Section 13.2](#), [Section 13.3](#), [Section 13.4](#), [Section 13.5](#) and [Section 13.6](#), respectively.

Imputation methods for missing overall scores (including missing data due to intercurrent events [Section 8.1](#)) for the analyses of primary and secondary endpoints are listed as below. The estimand corresponding to these analyses are described in [Section 8](#).

Efficacy Endpoints	Statistical Analysis Type	Statistical Analysis Methods	Imputation Methods
Primary	Primary	MMRM	Imputation: maximum likelihood estimation
	Sensitivity 1	MMRM	Imputation: maximum likelihood estimation
	Sensitivity 2	MMRM	Imputation: J2R
	Sensitivity 3	MMRM	Imputation: maximum likelihood estimation
	Sensitivity 4	MMRM	Imputation: maximum likelihood estimation
	Supplemental 1	Trimmed Mean using ANCOVA	Imputation: worst score
	Supplemental 2	MMRM	Imputation: maximum likelihood estimation
Secondary (continuous)	Secondary	MMRM	Imputation: maximum likelihood estimation
	Sensitivity	MMRM	Imputation: J2R
	Supplemental	Trimmed Mean using ANCOVA	Imputation: worst score
Secondary (binary)	Secondary	Logistic model	Imputation: NRI

MMRM=mixed model for repeated measures; ANCOVA= analysis of covariance; J2R=Jump to reference; NRI= nonresponse imputation

For other binary efficacy endpoints (e.g. QMG responder), missing data will be imputed using nonresponse imputation (NRI). That is, study participants with missing data at the timepoint of interest, and all timepoints after use of rescue medication will be treated as non-responders.

For ordinal endpoints (EQ-5D-5L, PGI-S, PGI-C), the observed case method will be applied. No further imputation is used.

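### An End of Study visit done early in the Observation Period would be summarised as Day 99, because the SAP has no date rule for it

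*SAP*

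**What the plan says.** SAP 3.2.1 sets the rule for all analyses: "All data will be analyzed based on the visits identified per the Schedule of Activities in protocol". It continues: "Mapping to analysis visit windows is not applied, except for premature end of treatment (PEOT) visits". Section 3.2.3 then gives the mapping for premature end of treatment (PEOT) assessments and for nothing else.

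The Schedule of Activities (Protocol 1.3) has one EOS column, Visit 14, at Day 99±4. Elsewhere the protocol allows that visit at other times:

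- Participants who complete treatment and then need rescue during observation "may either opt to receive IVIg or PEX or complete the End of Study (EOS) visit and immediately roll over into an OLE study" (Protocol 1.1, repeated in 4.1 item 5).
- For participants already rescued during treatment who need a second course and choose the open-label study, Protocol 4.1 item 6 states: "The EOS visit must be completed before enrolling into an OLE study".
- Protocol 4.4 states: "Study participants will have an EOS Visit performed 8 weeks after the last dose of study medication, or upon discontinuation of the study".

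Protocol 4.2 justifies the 8-week Observation Period by the recovery of IgG and of AChR and MuSK antibodies, "as well as monitoring the sustainability of the clinical effects after discontinuation".

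For binary endpoints other than the Day 43 responder, SAP 4.2.1 says that "study participants with missing data at the timepoint of interest, and all timepoints after use of rescue medication will be treated as non-responders".

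**The concern.** The SAP recognises that a visit brought forward needs reassigning, and does so for PEOT. It gives no such rule for EOS, which can be brought forward in the same way. Read as written, an EOS visit on Day 57 takes the Visit 14 label and appears in tables and mean plots as Day 99.

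Three things are at stake.

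- **Off-drug course.** QMG, MG-C, MG Symptoms PRO, PGI-S, PGI-C, total IgG and autoantibodies are scheduled in the Observation Period only at Visits 12 and 14. Anti-tetanus titre and IgA/IgM/IgE are scheduled there only at Visit 14. Day 99 is therefore one of two off-drug points, or the only one.
- **Selection.** Many of the participants concerned leave because they have worsened, so the mistimed values are not a random subset. Their share could differ between arms.
- **Responders.** The non-responder rule is triggered by a missing value or by rescue medication. A participant who rolls over without IVIg or PEX triggers neither if the early EOS fills Visit 14.

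**Working it through.** The plan states no figure for this point, so there is none to reproduce. The check is of the rules, then of the timing, then of the possible size.

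**1. Does any other rule move an early EOS?**

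- SAP 3.2.3: PEOT assessments only.
- SAP 8.1: maps observation-phase data to the nearest visit, but only for participants who stopped treatment or withdrew during the Treatment Period, and only for the primary analysis.
- SAP 4.3: prefers scheduled to unscheduled values and has no check on dates.
- SAP 5.1: counts roll-over for rescue as a discontinuation sub-category and attaches no data rule.

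None applies to a treatment completer who leaves during observation.

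**2. How far out can the label be?** Nominal days from the Schedule: last dose (Visit 9) Day 36, Visit 10 Day 43, Visit 14 Day 99 with window 95 to 103. The Observation Period starts the day after the Treatment Period ends (SAP 3.2.2), so nominally Day 44.

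- Earliest EOS: 99 − 44 = 55 days before Day 99, and 95 − 44 = 51 days before the window opens.
- EOS on Day 57: 99 − 57 = 42 days out. It is 57 − 36 = 21 days after the last dose, against 99 − 36 = 63 days for a true Day 99 value.
- EOS at 8 weeks after the last dose (Protocol 4.4): 36 + 56 = Day 92, which is 3 days before the Schedule's window opens. The two passages do not agree.

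**3. Responder example.** A participant is 6 points better than Baseline on MG-ADL at Day 43 and 3 points better at an EOS on Day 57. The loss of 3 points exceeds the protocol's example of worsening (2 points), yet 3 ≥ 2 still meets the responder definition. Labelled Visit 14, this is a Day 99 responder. Placed by date, Visit 14 is missing and the imputed analysis counts a non-responder. SAP 2.4 plans 30 participants per dose group in Stage 1 and 30 to 50 in Stage 2, so 60 to 80 in an arm carried through both. Each such participant then moves the imputed rate by 100/80 = 1.25 to 100/60 = 1.7 percentage points.

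**4. Illustration for means.** Shift in the Day 99 mean = f × d, where f is the share of Visit 14 records that are early EOS and d is the early value minus the true Day 99 value. Both are assumptions; the documents give neither. The upper value for IgG is the maximal reduction of about 43% after sc dosing in UP0018 (Protocol 4.2).

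| f | IgG shift in percentage points, d = −10 to −43 | MG-ADL shift in points, d = +2 to +4 |
|---|---|---|
| 5% | −0.5 to −2.1 | +0.1 to +0.2 |
| 20% | −2.0 to −8.6 | +0.4 to +0.8 |
| 40% | −4.0 to −17.2 | +0.8 to +1.6 |

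The IgG sign would suggest incomplete recovery. The MG-ADL column assumes that leavers would have been better by Day 99 than on the day they left; if they would have worsened further, its sign reverses.

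**The case against.** **The Visit 14 label is inferred.** No sentence says that an early EOS is Day 99, and the case report form's visit coding is not in the documents. This is correct. The inference is still the natural one: data follow the Schedule's visits, the Schedule has one EOS visit, and windowing is excluded. If another handling is intended, the SAP needs to state it.

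**Nothing confirmatory is touched.** This stands. The primary and all secondary efficacy endpoints are at Day 43. A reader might infer that the trial's efficacy conclusion is at risk; the documents do not support that. The affected outputs are descriptive, although several are listed protocol endpoints for the Observation Period.

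**The problem can be seen.** SAP 5.1 tabulates roll-over for rescue and participant counts by visit. SAP 3.2.1.1 defines relative day for listings, and responder tables show observed and imputed results separately. This helps a reader trace individual cases but does not correct a by-visit table or plot.

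**The large end of the illustration is unlikely.** This also stands. It pairs the largest exit share with the deepest IgG suppression. Protocol 4.3 links IgG reduction to symptom improvement, so participants leaving for worsening may well have recovering IgG.

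**Mapping to the nearest visit would not be enough.** This is right, and it shapes the fix. For anti-tetanus titre and IgA/IgM/IgE the nearest Observation visit is Visit 14 itself. For measures scheduled only at Visits 12 and 14 (midpoint Day 85), an EOS on Days 86 to 94 also returns to Visit 14. An EOS on Day 75 after a Visit 12 on Day 71 puts two values in one slot. Moving leavers out of Day 99 also leaves means of those who did not leave for worsening.

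**Conclusion.** The point holds in a limited form. Under SAP 3.2.1 as written, an early EOS assessment would be summarised as Day 99, with a timing error of up to about 8 weeks (55 days nominally). That distorts the descriptive Day 99 summaries of MG-ADL, QMG, MG-C, MG Symptoms PRO, PGI-S/PGI-C, IgG, autoantibodies, IgA/IgM/IgE and anti-tetanus titre. It can also turn a participant who left for worsening into a Day 99 responder, provided no IVIg or PEX was given and the score is still at least 2 points better than Baseline.

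The conclusion rests on reading the single EOS column as the label for every EOS visit. It would be tempting to say that the Day 99 results are materially wrong, or biased between arms. The documents do not support either statement: they give no number, timing or distribution by arm of early exits, and the shifts shown above are illustrations. The correction is worth making because the outputs bear on a stated purpose of the Observation Period and the cost is small.

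**What to change.** Amend SAP 3.2.1 and 3.2.3 as follows.

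1. Keep an EOS assessment at Visit 14 only if its actual date falls in a stated Visit 14 window. Set that window after reconciling the Schedule's Day 99±4 with the 8 weeks after last dose in Protocol 4.4 (nominally Day 92).
2. Otherwise assign it by date to an earlier Observation visit (Visits 11 to 13) at which that assessment is scheduled, if it falls in a stated window around that visit and the slot is empty. A scheduled value takes precedence.
3. If there is no such slot, show the value in a separate early-EOS row, not as Day 99. This will always apply to anti-tetanus titre and IgA/IgM/IgE. If the Schedule's own windows are used, an EOS on Day 57 could fill Visit 11 (Days 54 to 60) for MG-ADL, but for IgG or QMG it would go to the early-EOS row, since Visit 12 covers Days 67 to 75.
4. Treat Visit 14 as missing for these participants, so that the existing non-responder rule applies to binary endpoints.
5. Report the number and timing of early EOS visits by arm. Note beside the Day 99 means of continuous measures that they exclude participants who left for worsening.

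The cost is a short SAP rule and programming from visit dates. Fewer participants will appear at Day 99, and the selection described in item 5 remains and has to be stated.

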3.2.1.1 Relative day

Relative day for an event will be derived with the date of the first sc infusion of IMP as reference.

Relative days for an event of measurement occurring before the date of first sc infusion will be prefixed with '-' and are calculated as follows:

$$\text{Relative Day} = [(\text{Event Date} - \text{Date of First Infusion})]$$

The relative day for an event or measurement occurring on or after the reference date to the date of the last infusion is calculated as follows:

$$\text{Relative Day} = [(\text{Event Date} - \text{Date of First Infusion}) + 1]$$

For events or measurements occurring after the date of the last sc infusion, relative day will be prefixed with '+' in the data listings and will be calculated as follows:

$$\text{Relative Day} = + [(\text{Event Date} - \text{Date of Last Infusion})]$$

There is no relative Day 0. Relative day is not calculated for partial dates in cases where relative day is shown in a participant data listing. In such cases, relative day should be presented as '- -' in the participant data listings.

3.2.2 Study periods

The maximum duration of the study per participant will be approximately 18 weeks, consisting of the following 3 periods:

- Screening Period: 1 to 28 days
- Treatment Period: 6 weeks
- Observation Period: 8 weeks

The end of the study is defined as the date of the last visit of the last participant in the study.

The following definitions for starting and entering the study periods will be applied:

- **Treatment Period** starts with the first day of IMP and ends after Day 43/PEOT assessments. All participants in the Safety Set will be considered to have started the Treatment Period. A participant is considered to have completed the Treatment Period if assessments from Treatment Period Day 43 are completed.
- **Observation Period** starts one day after the end of the Treatment Period and ends after the final assessments on the last visit. Participants with assessment on any Observation Period day are considered to have started the Observation Period. Participants who have a completed status in the study termination case report form are considered to have completed the Treatment and Observation Periods.

